#### **9.10.11. Comprehensive Physical Examination & Targeted Physical Examination**

Physical examinations must be performed by a physician, physician assistant, or registered nurse practitioner.

A comprehensive physical examination must be performed as indicated in [Table 4](#) and as documented within the medical record. The comprehensive physical examination must include the following organ or body system assessments: head, eyes, ears, nose, throat, musculoskeletal, cardiovascular, lymphatic, respiratory, abdomen, skin, extremities, and neurological.

Assessments of any specific signs or symptoms reported by the patient must also be performed and documented along with any other findings of note. Clinically significant findings at Screening must be addressed in medical history, (i.e., findings should be attributable to a diagnosis recorded in medical history). Following the examination at Screening, new or changed physical examination findings meeting the definition of an adverse event must be reported as an adverse event. If possible, the same individual should perform each physical examination on a patient during the study.

Targeted physical examinations are symptom-directed examinations and involve the organ system(s) associated with the symptoms exhibited or reported. Targeted physical examinations are to be performed at visits indicated in [Table 4](#). If the investigator observes no symptoms that warrant further examination, the investigator may forego a more detailed physical examination, and the targeted physical examination may be considered complete.

**9.10.12. Pregnancy Test**

WOCBP (see Section 9.8) will complete a pregnancy test as indicated in Table 4, or at any time if pregnancy is suspected. Negative test results are required on Day 1 before study drug administration. Women of child-bearing potential will require a serum pregnancy test (hCG-Qual) at the Screen A visit or at any point in time if a pregnancy is suspected.

See Section 9.8.3 for a description of procedures to be followed in case of pregnancy.

**9.10.13. Study Drug Administration**

For dose levels up to 20 mg, patients should self-administer one capsule orally once a day beginning on Day 1 (in clinic) through the end of the Treatment Period, as indicated in Table 4. Patients who dose escalate to 30 mg should administer two capsules orally once a day. Each dose of study drug should be administered at approximately the same time each day. Study drug administration should be recorded in a patient diary through Week 100.

A vomited dose must not be replaced. A double dose (e.g., missed dose from previous day and dose for current day) must not be taken.

Refer to Section 9.4 and 9.11 for treatment compliance and detail in dose management.

**9.10.14. Study Drug Dispensation and Collection**

Study drug will be dispensed to the patient and collected from the patient as indicated in Table 4. The patient will be dispensed the appropriate number of treatment kits at each timepoint: Day 1, Week 2, Week 4, Week 6, Week 8, Week 12, Week 24, Week 36, Week 48, Week 52 (B), Week 64, Week 76, and Week 88. If the patient is provided more than one kit, only one treatment kit should be opened at a time. Dispensed treatment kits from each visit (including unscheduled visits) should be returned to the site for collection as indicated in Table 4 or at the subsequent visit.

If the appropriate number of treatment kits (e.g., a 3-month supply) cannot be dispensed as outlined in Table 4, a partial supply may be provided to the patient. The remainder may be provided separately to the patient. Every effort should be made to avoid interruptions in dosing.

**9.10.15. Telephone Contact**

Patients will be contacted by telephone as indicated in Table 4. Patients will be asked about their body weight and other signs of fluid retention, as well as AEs and any changes to concomitant medications. If fluid retention is suspected, the patient should be instructed to stop taking study medication immediately and be medically evaluated by the investigator or a local physician within 1 to 2 days, as detailed in Section 9.1.1.

**9.10.16. Adverse Event Collection**

Patients will be observed for general appearance, presence of illness or injury, or signs indicative of a concurrent illness as indicated in Table 4. Patients must be instructed to volunteer any information regarding AEs on or after the first dose of study drug, or sites may query the patients with an open question regarding any AEs they may be experiencing (e.g., “How have you been feeling since your last visit?”). Any findings are to be documented. Patients must be asked if they have been hospitalized, had any accidents, used any new medications, or changed

concomitant medication regimens (including prescription drugs, over-the-counter medications, vitamins, herbal products, and minerals). Responses must be documented in the source documents.

AEs should be reported from the time of the first dose until the Week 112 (B) visit as indicated in Table 4.

For patients who discontinue study drug early (prior to Week 100) and continue to be followed in the study, all AEs should be recorded for 12 weeks following the patient's last dose of study drug. Beyond 12 weeks after the patient's last dose, only those AEs that are relevant to the clinical condition including kidney disease, may have an impact on kidney function, or may impact the interpretation of safety or efficacy data must be recorded in the AE log within the EDC. Unscheduled phone visits may be used, as necessary, to ensure accurate collection of AEs of interest.

AEs that are related to study procedures should be recorded in the AE log within the EDC independent of the patient's study drug status or duration since the patient's last dose of study drug.

See Section 11 for more detail regarding adverse events.

#### **9.10.17. Kidney Ultrasound**

Kidney ultrasound (historical or an ultrasound performed at Screen A) may be used to diagnose ADPKD. Patients with prior diagnosis of ADPKD will not have a kidney ultrasound performed as part of the study but must provide documentation of ADPKD diagnosis for eligibility.

#### **9.10.18. Virus Serology**

Blood samples will be collected for testing for hepatitis B and hepatitis C as indicated in Table 4. If the initial hepatitis C result is positive, then the patient will need to return for an unscheduled hepatitis C virus ribonucleic acid (HCV RNA) assessment to determine if the virus is present at the current time. If the results of this test are negative, the patient may continue in the screening process.

#### **9.10.19. Clinical Chemistry**

Samples will be collected for the following clinical chemistry analyses as indicated in Table 4: ferritin, creatine kinase (CK), BUN, enzymatic creatinine, eGFR, TBL, direct bilirubin, ALT, AST, ALP, sodium, potassium, calcium, phosphorus, uric acid, total protein, glucose, albumin, lactate dehydrogenase (LDH), magnesium, chloride, bicarbonate, and GGT.

##### **9.10.19.1. eGFR**

The equation used to calculate eGFR for each patient (CKD-EPI or Bedside-Schwartz) is based on the patient's age at the time of consent/assent (generally the Screen A visit). For Adults ( $\geq 18$  years  $\geq 70$  years) eGFR will be calculated by a central laboratory at the Screen A and Screen B visits using the Chronic Kidney Disease Epidemiology Collaboration (CKD-EPI) equation:

$$\text{eGFR (mL/min/1.73 m}^2\text{)} = 141 \times \min(S_{\text{cr}}/\kappa, 1)^{\alpha} \times \max(S_{\text{cr}}/\kappa, 1)^{-1.209} \times 0.993^{\text{Age}} \times 1.018 \text{ [if female]} \times 1.159 \text{ [if black]}$$

For Adolescents ( $\geq 12$  and  $< 18$  years):

- eGFR will be calculated by a central laboratory at the Screen A and Screen B visits using the Bedside Schwartz equation:

$$\text{eGFR (mL/min/1.73 m}^2\text{)} = (0.41 \times \text{Height in cm}) / S_{\text{cr}}$$

Where  $S_{\text{cr}}$  is serum creatinine (mg/dL),  $\kappa$  is 0.7 for females or 0.9 for males, and  $\alpha$  is -0.329 for females or -0.411 for males. Min indicates the minimum of  $S_{\text{cr}}/\kappa$  or 1 and max indicates the maximum of  $S_{\text{cr}}/\kappa$  or 1. Age indicates age at time of lab collection.

The eGFR values collected at Screen A and Screen B visits will be averaged to determine eligibility. The two eGFR values used to determine eligibility must have a percent difference  $\leq 25\%$ , as determined by the following calculation:

$$\text{Percent Difference} = |X-Y| / ((X+Y)/2)$$

$$X = 1^{\text{st}} \text{ eGFR value (Screen A)}$$

$$Y = 2^{\text{nd}} \text{ eGFR value (Screen B)}$$

$$|X-Y| = \text{absolute value of the difference between the two eGFR values}$$

In the absence of any clinically significant event or other medical conditions, the investigator should consider re-testing eGFR if the most recent value is significantly different from the prior value.

#### **9.10.20. N-Terminal Pro-Brain Natriuretic Peptide (NT-Pro BNP) and Brain Natriuretic Peptide (BNP)**

Samples will be collected for NT-Pro BNP and BNP as indicated in [Table 4](#). As recent exercise may affect BNP and NT-Pro BNP levels, patients should be allowed to rest for one hour following arrival at the clinic and prior to obtaining this blood sample. This sample must be taken with the patient in the same position at all appropriate visits, e.g., sitting or semi-recumbent.

Detailed instructions on collection, storage and shipment of the sample will be provided in the Central Laboratory Manual provided to the investigator.

#### **9.10.21. Hemoglobin A1c**

Samples will be collected for hemoglobin A1c as indicated in [Table 4](#). Detailed instructions on collection, storage, and shipment of the samples will be provided in the Central Laboratory Manual provided to the investigator.

**9.10.22. Hematology**

Samples will be collected for the following hematology assessments as indicated in Table 4: hematocrit, hemoglobin, red blood cell (RBC) count, white blood cell (WBC) count, neutrophils, bands (if detected), lymphocytes, monocytes, basophils (if detected), eosinophils (if detected), absolute platelet count, mean corpuscular hemoglobin (MCH), mean corpuscular volume (MCV), and mean corpuscular hemoglobin concentration (MCHC).

**9.10.23. Coagulation**

Samples will be collected for the following coagulation assessments as indicated in Table 4: Prothrombin Time (PT) and International Normalized Ratio (INR). The coagulation assessments were added to the schedule of assessments through a protocol amendment. Sites should collect these samples from patients once the central laboratory kits and database enable collection. Until such time the site can collect this test, failure to collect it is not considered a protocol deviation.

**9.10.24. Lipid Panel**

Samples will be collected for the following lipid assessments as indicated in Table 4: Total Cholesterol, Low-Density Lipoprotein (LDL), High-Density Lipoprotein (HDL), and Triglycerides.

The lipid panel was added to the schedule of assessments through a protocol amendment. Sites should collect these samples from patients once the central laboratory kits and database enable collection. Until such time the site can collect this test, failure to collect it is not considered a protocol deviation.

**9.10.25. SARS-CoV-2 Antibody Testing**

Samples will be collected for SARS-CoV-2 antibody testing as indicated in Table 4.

The SARS-CoV-2 antibody testing was added to the schedule of assessments through a protocol amendment. Sites should collect these samples from patients once the central laboratory kits and database enable collection. Until such time the site can collect this test, failure to collect it is not considered a protocol deviation.

**9.10.26. Urinalysis and Microscopy**

Samples will be collected for the following urinalysis and microscopy assessments as indicated in Table 4: specific gravity, ketones, pH, protein, blood, glucose, clarity, color, leukocytes, nitrite, bilirubin, and a microscopic examination (if indicated based on laboratory results).

**9.10.27. Urine Collection for Albumin to Creatinine Ratio (ACR)**

Albumin/creatinine ratio will be measured by first morning void spot urine collection as indicated in Table 4. Appropriate containers for the collection will be provided to the patient at the visit prior to the collection.

Patients should be instructed how to properly capture a sample of their first morning void, defined as their first urination after 5 AM. Following Day 1, if a patient presents for a visit and has forgotten to collect (or bring) the urine sample(s) for that visit, they may return within 7 days to submit the sample(s) collected that day.

[REDACTED]

[REDACTED]

[REDACTED]

[REDACTED]

**9.10.32. Pharmacokinetic (PK) Blood Samples**

Blood samples for determination of plasma bardoxolone methyl and potential metabolite concentrations will be drawn as indicated in Table 4.

Patients must provide the time of their last two doses of study drug.

PK blood sample collection instructions should be referenced in the Central Laboratory Manual.

The date and time of collection of all PK blood samples should be recorded; however, any deviations from the protocol-specified sampling times will not be considered protocol deviations. Sample time deviations will be summarized in the study report. Dates in the case report form should be recorded in an unambiguous format (e.g., DD MMM YYYY) and time should be recorded to the nearest minute (e.g., HH:MM using the 24-hour clock). Blood samples not drawn should be recorded as such.

Patients who have discontinued study drug should not complete PK procedures

Week 12 PK

If sites or patients are unable to perform the required PK assessments at the Week 12 visit, these PK assessments may be collected at Week 24, Week 36, or Week 48.

Patients must refrain from taking study drug prior to coming to the clinic for the Week 12 visit, as patients will administer study drug in-clinic as instructed by the site. Patients must provide the time and date of the two most recent doses of study drug, prior to the blood samples being collected.

Sites should obtain the 0-hour (pre-dose) PK sample, then instruct the patient to administer study drug. Blood samples for PK analysis should then be drawn at 2 and 4 hours post dose administration.

#### Week 100 PK

Patients must be instructed to refrain from taking study drug prior to coming to the clinic for the Week 100 visit, as patients will administer study drug in-clinic as instructed by the site. Patients must provide the time and date of the two most recent doses of study drug, prior to the blood samples being collected.

Patients will have blood drawn at a single timepoint (i.e., pre-dose) for PK analysis at this visit.

Sites should obtain the 0-hour (pre-dose) PK sample, then instruct the patient to administer the final dose of study drug in-clinic.

#### Week 103, Week 104 (B), and Week 108 (B) PK

These PK assessments occur during the Off Treatment Period, so no study drug administration is associated with these assessments.

Patients will have blood drawn at a single timepoint for PK analysis at this visit.

### **9.10.33. Ambulatory Blood Pressure Monitoring**

For adult patients, Ambulatory Blood Pressure Monitoring (ABPM) is an optional sub-study conducted at the timepoints specified in Table 4. To participate, patients must have a baseline ABPM assessment. The baseline assessment must occur during the screening period, ideally 2-3 days prior to Day 1. The additional assessments occur at the following time points: Week 12, Week 48, and between Weeks 88 and 100 (prior to the patient's last dose of study drug), as defined in [Table 4](#).

Participation in the ABPM sub-study is optional; however, patients should be encouraged to participate, and use of home health visits is strongly encouraged to minimize the burden on the patient and to maximize participation.

To ensure a sufficient volume of ABPM data, the Sponsor may halt enrollment of patients not participating in the ABPM sub-study. Participation will be monitored closely as overall enrollment progresses, and the Sponsor will update sites on progress toward achieving sufficient ABPM participation.

A Sponsor-provided device will be placed on the patient by the study team, and the patient must wear the device for approximately 24 hours.

Upon completion of the 24-hour period, the site will collect the device from the patient and ABPM data will be sent to the central vendor to determine if the 24-hour recording passes the validity criteria. The criteria used to define a valid ABPM session for sites to determine the need for a repeat 24-hour session, if possible, are:

- At least 70% of planned inflations are successful during the overall recording session;
- At least 18 hours of analyzable data, and;
- Not more than two consecutive hours of missing data.

For detailed instructions regarding ABPM refer to the study reference manual.

The addition of ABPM to the schedule of assessments occurred through a protocol amendment, and site and patient participation will be offered, once available.

### **9.10.34 Tanner Staging**

Gender appropriate Tanner staging will be performed on all patients who enroll in the study as adolescents. Tanner staging should be performed at Day 1, Week 52 (B), and Week 108 (B), as outlined in [Table 4](#), to monitor and assess sexual maturity. All assessments must be performed even if a patient reaches 18 years of age while participating in the study. Tanner staging may be performed only by a physician (specifically, the principal investigator or sub-investigator). For further guidance and to access the Tanner Staging see the Study Reference Manual.

## **9.11. Dose Management**

### DOSE ESCALATION

Both adult and adolescent patients randomized to placebo will remain on placebo throughout the study, undergoing sham titration. Both adult and adolescent patients receiving study drug will start with once-daily dosing at 5 mg and will dose-escalate to 10 mg at Week 2, to 20 mg at Week 4, and then to 30 mg at Week 6 (only if baseline ACR > 300 mg/g) unless contraindicated clinically and approved by the Medical Monitor.

Dose escalation may need to proceed more slowly if the patient experiences early elevations in ALT/AST over ULN, e.g. at Week 2 (see Section [9.1.2](#)) or if the patient misses visits (see Section during the Dose Escalation Period). The dosing objective is to titrate patients to the maximum dose determined by baseline ACR and maintain the maximum dose after initial dose-titration. The investigator should discuss any reason for not dose-escalating at Weeks 1, 2, 4, or 6 with the Medical Monitor. In cases where dose escalation is delayed or not achieved, the investigator should consider dose escalation to goal dose at any time throughout the dosing period.

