#### **5.1.2.2. Transaminase and Gamma-Glutamyl Transpeptidase (GGT) Elevations**

In clinical studies of bardoxolone methyl, almost all patients had increases of transaminase enzymes above baseline upon initiation of treatment, which followed a consistent pattern. These increases were not associated with elevations in bilirubin, and hepatotoxicity has not been observed. In BEACON, fewer hepatobiliary SAEs were observed in the bardoxolone methyl arm than in the placebo arm. The elevations begin immediately after initiation of treatment or an increase in dose; they peak approximately two to four weeks later. In most patients, transaminase elevations were mild, but approximately 4% to 11% of patients experienced an elevation greater than 3X the upper limit normal (ULN). The elevations resolved to levels less than the ULN in most patients with elevations, within two weeks after peak values while patients continued taking study drug. Patients who experienced elevations to greater than 3X the ULN sometimes required additional time to resolve. While some patients have had elevations to

above 3X the ULN, persistent elevations to above 3X the ULN have not been observed, and the elevations did not recur once resolved, unless caused by other factors.

Bardoxolone methyl regulates gamma-glutamyl transpeptidase GGT, a known Nrf2 target gene protein. In clinical studies, low level GGT elevations during treatment were common, mild, and typically lasted longer than alanine aminotransferase (ALT)/ aspartate aminotransferase (AST) elevations. Bilirubin levels in patients experiencing transaminase or GGT elevations due to treatment with bardoxolone methyl either remained at baseline levels or decreased. The ALT, AST, and GGT elevations were generally self-limiting in patients who continued treatment with study drug.

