### 9.7. Unscheduled Visits

Unscheduled visits may be performed at any time and for any reason, including those not specifically mentioned in this section, as deemed necessary by the investigator.

Unscheduled visits conducted for the following reasons should include collection of AEs, clinical chemistry, BNP/NT-proBNP, hematology, concomitant medication collection, and vital signs:

- Assessment of weight gain per Section 9.1.1;
- Management of an AE or SAE;
- Performance of additional laboratory tests for clinically abnormal laboratory test values or to confirm a possible pregnancy;
- Dose re-escalation;
- Dose de-escalation;
- Resuming study drug following an extended interruption;

- eGFR  $\leq$ 15.0 per Section 9.1.9;
- Patient safety evaluation.

Unscheduled visits conducted for the following reasons do not require additional assessments unless deemed necessary by the investigator:

- Study drug dispensation;
- Placement or return of ABPM monitor;
- Any operational need that would require the patient to return to the site between scheduled visits.

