### DOSE DE-ESCALATION AND RE-ESCALATION

The investigator may choose to decrease the patient's dose to the prior dose (e.g., 20 mg to 10 mg, or 10 mg to 5 mg), if clinically indicated. Dose de-escalation may occur more than once, but the minimum dose permitted is 5 mg. Reasons for dose de-escalation should be discussed with the Medical Monitor prior to changing the dose and must be documented. After dose de-escalation, patients must return for an unscheduled office visit within 4 weeks ( $\pm$  3 days) to perform the assessments detailed in Section [9.7](#).

If a patient's dose has been reduced, dose re-escalation back to a higher dose is permitted to meet the dosing objective. However, patients who dose re-escalate must have a telephone call 1 week after dose re-escalation and an unscheduled office visit 2 weeks ( $\pm$  3 days) after dose re-escalation to perform assessments detailed in Section [9.7](#).

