## RESUMING STUDY DRUG

Any patient who interrupts study drug for 14 consecutive days or more must have approval from the Medical Monitor prior to resuming study drug.

When a patient resumes study drug, after an extended interruption (e.g., more than 14 days), the site should discuss the appropriate starting dose and visit frequency with the Medical Monitor. The duration of the interruption and the reason for interruption should be taken into consideration when determining how to safely resume study drug. Following an extended interruption, when the investigator deems it is safe for the patient to return to the site for an in-person visit, the investigator should conduct an evaluation to determine whether the patient is still eligible to receive study drug and to determine the appropriate dose, in consultation with the Medical Monitor. This should include a confirmation that the patient's circumstances have not changed in a manner that would prohibit administration of the study drug (e.g., the patient is now taking an excluded medication). Once the investigator determines study drug administration is appropriate, dosing may proceed.

Patients must have a telephone call 1 week after resuming and an unscheduled office visit 2 weeks ( $\pm$  3 days) after resuming study drug to perform assessments detailed in Section 9.7.

For additional guidance on resuming drug following a positive COVID-19 test, see Section 9.11.5

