### **9.11.1. Dose Escalation Period – Missed In-Person Visits**

The first 8 weeks of the trial require intense safety monitoring of patients as they progress through the dose-escalation period of the study. When in-person visits are not be feasible, due to COVID-19 or any other reason, patients who are in the dose escalation period of the study should remain on their current study drug dose. The dose at the last in-person visit, if not the goal dose, will be considered the maximum dose until completion of dose-escalation can be safely resumed (See Section 9.11.5).

Protocol specified in-clinic follow-up visits, for safety/tolerability, must be completed where possible. Required assessments for patients who are unable to have an in-person visit are described in Appendix 2.

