### **9.11.5. Resuming Study Drug After COVID-19 Interruption**

Patients who interrupt study drug due to a positive COVID-19 test may resume study drug without an in-clinic visit, at the investigator's discretion, if COVID-19 symptoms are mild, and if the duration of interruption did not exceed 14 days.

Study drug may be resumed when the patient no longer presents an active infection (defined as resolution of symptoms or a negative SARS-CoV-2 test), as assessed by the Investigator and/or the patient's physician(s). If COVID-19 symptoms persist (e.g., loss of taste or smell), the patient should be encouraged to repeat SARS-CoV-2 testing in order to minimize the duration of study drug interruption.

For more information related to study drug management and COVID-19 see Appendix 1, Section 4.5.

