#### **4.5 Resuming or Dose-escalating Study Drug after Interruptions or Changes**

Refer to Section [9.11.5](#).

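### A delayed first dose escalation has no required follow-up, so the next chemistry can be 84 days away, well past the expected transaminase peak

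*Protocol*

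**What the plan says.** The planned titration goes from 5 mg to 10 mg at Week 2, 20 mg at Week 4 and, if baseline ACR exceeds 300 mg/g, 30 mg at Week 6. Protocol Section 9.11 then distinguishes three kinds of later dose increase:

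- **Delayed first escalation** (Dose Escalation): "In cases where dose escalation is delayed or not achieved, the investigator should consider dose escalation to goal dose at any time" during dosing. No follow-up is attached. The investigator is asked to discuss with the Medical Monitor why a planned step was not taken.
- **Re-escalation after a reduction** (Dose De-Escalation and Re-Escalation): "patients who dose re-escalate must have a telephone call 1 week after dose re-escalation and an unscheduled office visit 2 weeks" (±3 days) later, with the Section 9.7 assessments.
- **Resumption** (Resuming Study Drug): "Patients must have a telephone call 1 week after resuming and an unscheduled office visit 2 weeks" (±3 days) later, again with the Section 9.7 assessments.

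Section 9.7 lists the unscheduled visits that "should include collection of AEs, clinical chemistry, BNP/NT-proBNP, hematology, concomitant medication collection, and vital signs". The list names re-escalation, de-escalation and resumption after an extended interruption, but not a delayed first escalation. A visit made only to dispense drug needs no assessments unless the investigator wants them.

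For escalation held up by missed visits, Section 9.11.1 keeps the current dose "until completion of dose-escalation can be safely resumed (See Section 9.11.5"). Section 9.11.5 deals only with restarting after infection: "Patients who interrupt study drug due to a positive COVID-19 test may resume study drug without an in-clinic visit" under stated conditions. It refers on to Appendix 1 Section 4.5, titled "Resuming or Dose-escalating Study Drug after Interruptions or Changes", which refers back to Section 9.11.5.

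On liver enzymes, Section 5.1.2.2 states: "The elevations begin immediately after initiation of treatment or an increase in dose; they peak approximately two to four weeks later". Section 9.1.2 expects nearly all such rises to be asymptomatic.

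**The concern.** A patient moving to a higher dose for the first time has shown less tolerance of it than one returning to a dose already taken, yet has less required follow-up. The transaminase rules in Table 5 (recheck within 48 to 72 hours above 3 times ULN, interrupt above 8 times ULN) act on a laboratory value. Where rises are expected to cause no symptoms, they cannot act unless blood is drawn. Section 5.1.2.2 reports that about 4% to 11% of patients exceeded 3 times ULN.

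The patients affected are those delayed for milder ALT/AST rises, missed visits or other reasons. Those who met the Table 5 interruption criteria restart at 5 mg and so fall under the resumption and re-escalation rules already.

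**Working it through.** The plan gives no figure of its own to reproduce. The check compares the rules and then does date arithmetic on Table 4.

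**1. What triggers a required blood test**

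| Dose increase | Required call | Required visit with chemistry and BNP |
|---|---|---|
| Re-escalation after reduction | 1 week | 2 weeks ±3 days |
| Resumption | 1 week | 2 weeks ±3 days |
| Delayed first escalation | none | none |

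After a delayed first escalation, the next required test is therefore the next scheduled visit. The last scheduled call is on Day 45.

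**2. Time to the next scheduled chemistry and BNP**

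Target days from Table 4: Week 6, 42; Week 8, 56; Week 12, 84; Week 24, 168; Week 36, 252; Week 48, 336; Week 52, 364 (all ±3 days); Week 64, 448; Week 76, 532; Week 88, 616 (all ±5 days); Week 100, 700 (−5/+0 days).

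Nominal gap = next target − this target. Shortest gap = earliest next visit − latest this visit. Longest gap = latest next visit − earliest this visit. For Week 64 to Week 76: 532 − 448 = 84; 527 − 453 = 74; 537 − 443 = 94.

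| Escalation made at | Nominal gap (days) | Range with windows (days) |
|---|---|---|
| Week 6 | 14 | 8 to 20 |
| Week 8 or Week 48 | 28 | 22 to 34 |
| Weeks 12, 24, 36 | 84 | 78 to 90 |
| Week 52 | 84 | 76 to 92 |
| Weeks 64, 76 | 84 | 74 to 94 |
| Week 88 | 84 | 74 to 89 |

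Seven of the eight scheduled visits from Week 12 to Week 88 are followed by the 84-day gap; Week 48 is the exception.

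**3. Against the expected peak**

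The peak is expected 14 to 28 days after the increase. Even the shortest 84-day gap under the windows, 74 days, ends 74 − 28 = 46 days after that range closes. Section 5.1.2.2 also says most rises fall below ULN within two weeks after the peak, that is by about 28 + 14 = 42 days. A sample at 84 days would usually show neither the peak nor its decline.

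**4. Escalation between visits**

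Within each 84-day interval, 84 − 28 = 56 days lie more than 28 days before the next scheduled chemistry. Over Day 84 to Day 699 that is 7 × 56 = 392 of 616 days, or 64%.

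**5. With the existing rule applied**

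The next required chemistry falls at 14 days, at most 14 + 3 = 17.

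**The case against.** The strongest case on the other side has four parts.

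- **Ordinary delays are sampled.** A step taken late at Week 4 or Week 6 is followed by scheduled chemistry about 14 days later, with calls at Days 31, 38 and 45 on the schedule. At Week 8 the gap is 28 days. This stands, and confines the problem mainly to escalations from Week 12 on. The documents do not show how many occur.
- **The rises are mostly benign.** Section 5.1.2.2 describes them as mild in most patients and usually resolving on drug. It reports no persistent elevations above 3 times ULN and no hepatotoxicity. This limits the likely harm. It does not explain why the protocol requires a test after re-escalation and not after a first exposure to the higher dose.
- **Oversight continues.** Home weights are taken daily with stop rules (Section 9.1.1), the Medical Monitor should know why a step was missed, and Section 9.7 allows a visit for any reason, including patient safety evaluation. All true, but none requires blood to be drawn after a late escalation. The weights do cover much of the fluid risk. Section 5.1.2.1 ties that risk to the first three to four weeks of treatment, so the case rests on transaminases more than on BNP.
- **The 64% describes the calendar.** It treats every day as equally likely for a late step. Counting from Day 42 gives 392/658 = 60%. Either figure describes the visit schedule and not patient risk.

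It can also be said that reduction and interruption often have a clinical cause, while a missed step may only reflect a missed visit. The resumption rule is itself softened for interruptions of no more than 14 days with mild COVID-19. Both points are fair. Neither supplies a rule for the delayed first step.

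**Conclusion.** The gap is real and should be closed. A first escalation made from Week 12 on, other than at or shortly before Week 48 or late in a visit interval, has its next required chemistry after the expected peak. The worst case is 84 days nominally and 94 days at the window limits. The circular reference between Section 9.11.5 and Appendix 1 Section 4.5 means a site looking for the rule finds none.

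This rests on Table 4 as the only source of required chemistry after such a step, and on the protocol's own account of the timing and silence of transaminase rises. The number of patients affected is unknown, and serious harm is not predicted from the experience cited. The point does not bear on the sample size or the efficacy analysis. SAP Section 2 reports that sites were told on 10 May 2023 that development would stop, so the judgement is on the protocol as written.

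**What to change.** 1. In Section 9.11, apply the re-escalation follow-up (call at 1 week, visit with Section 9.7 assessments at 2 weeks ±3 days) to any dose increase made outside the planned Week 2, 4 and 6 steps, unless a scheduled visit already falls in that window.
2. Add delayed dose escalation to the Section 9.7 list of visits that carry laboratory tests.
3. Point Section 9.11.1 and Appendix 1 Section 4.5 to that rule instead of to Section 9.11.5.

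The cost is amendment wording, plus one call and one unscheduled visit for each patient escalated late. Sites already carry out the same procedures after a re-escalation.
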